11.2 Secondary Endpoints

11.2.1 *Time to death*

The time to death will be defined as the time from onset from symptoms until death from any cause. Patients who are alive or lost to follow-up at the cut-off date will be censored from this analysis.

11.2.2 *Mortality at 1 month*

1-month mortality is defined as the percentage of patients who have died 1 month from the time of start of treatment.

11.2.3 *Time to intubation*

The time to intubation will be defined as the time from symptom onset until time of intubation. Any patients already intubated at enrollment will be censored from this analysis.

11.2.4 *Time to improvement in oxygenation*

The time to improvement in gas exchange will be defined as the time from time of start of treatment until a $\geq 30\%$ decrease in oxygen requirement compared to

baseline [or elimination of oxygen requirement] without a decrease in SpO2 sustained for at least 48hrs or until discharge.

11.2.4 *Proportion of patients requiring ICU admission at 1 month.*

The proportion of patients requiring ICU admission will be calculated as the number of patients requiring ICU admission over the course of their hospitalization over the number of evaluable patients.

11.2.5 *Safety and Toxicity*

All subjects receiving at least one dose of the study drug will be evaluated for safety by monitoring symptoms, physical examinations, and laboratory tests. Adverse events will be classified and graded according to the NCI Common Toxicity Criteria version 5.0 (see Appendix A). The absolute number and frequency of each adverse event will be reported, and subdivided according to toxicity grade. A description of adverse events by treatment arm will also be reported. A particular adverse event occurring more than once in the same subject will be counted only once and at its worse grade.

11.2.6 *Duration of Hospitalization*

Duration of hospital admission will be measured from the time of admission until the time of discharge.

11.2.7 *7-point Ordinal Scale Score*

The mean/medians of the 7-point ordinal raw scores at day 14 from the start of treatment will be computed and compared between the treatment and control groups.

Exploratory Endpoints.

11.2.8 *Change in inflammatory markers from baseline*

Changes in LDH, D-Dimer, CRP, ESR, NLR and absolute lymphocytes before and after treatment and over time will be measured every other day during hospitalization.

11.2.9 *Change in circulating sIL-6 levels from baseline*

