11.2.12 Change in NEWS2 from baseline

Changes in NEWS2 score will be reported at days 3, 5, 8, 11, 15, and 29.

11.2.15 Change in IL-8 and downstream cytokines.

Circulating IL-8 and additional cytokines (IL1B, IL2, IL4, IL5, IL6, IL7, IL9, IL10, IFNgamma, TNFalpha and others) will be measured at baseline and at additional time points when possible (day 8, 15, 22, 29).

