13 STATISTICAL CONSIDERATIONS

13.1 Study Design and Sample Size

This study is a single-center, randomized open-label phase 2 trial to evaluate the efficacy and safety of anti-IL-8 in hospitalized adults with severe or critical COVID-19. The primary endpoint is time to improvement in clinical status: the time (days) required from the start of treatment to the improvement of clinical status (2 points) assessment from baseline based on the 7-point ordinal scale. Patients for whom there was no event will be censored.

Patients will be randomized in a 2:1 allocation ratio to either anti-IL-8 or standard of care. Patients will be assessed daily while hospitalized. Discharged patients will be contacted by telephone on Day 29 and then monthly up to one-year to assess status. In addition to these specific assessment times, one interim analysis is planned at and the DSMC will actively monitor interim data to make recommendations about early signs of overwhelming efficacy and futility/study closure (see Section 13.4.)

With a sample size of 138 patients: N=92 patients randomized to the treatment arm and N=46 patients assigned to the standard of arm/control, the study will have 80% power to detect an increase in median time to improvement from 2 days (control) to 5 days (treatment arm) with one-sided alpha of 0.025. The sample size was estimated based on a hazard ratio (HR) of 0.40 assuming an exponential survival distribution with inflation to account for one interim look and 5% drop-out rate.

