13.2 Study Endpoints and Analysis Plan

All subjects who receive at least one dose of study drug will be considered evaluable and included in the efficacy and safety analysis.

Analytic plan for primary objective:

The primary efficacy null hypothesis of the equality of time to improvement (2 points) in clinical status curves will be tested with the log-rank test. The overall type I error for the primary analysis will be considered one-sided alpha of 0.025. Kaplan-Meier estimates will be reported for each of the two arms with median time to improvement and 95% confidence intervals (CI). Cox regression will be employed to estimate the treatment effect (HR) and 95% CI.

Analytic plan for secondary and exploratory objective:

We will estimate the distributions of all time-to-event endpoints using the Kaplan-Meier method and if possible, provide medians (95% CI). Comparisons between survival curves will be assessed using log-rank tests and Cox regression models.

For each arm, we will estimate the 1-month mortality rate and incidence of adverse events graded by CTCAE v5.0 using the exact 95% confidence intervals. Comparisons between the two arms will be assessed using chi-squared or Fisher's exact tests. The mean/medians of the 7-point ordinal scores at day 14 after the start of treatment will be computed and compared between the two groups using two-sample t-test or the equivalent non-parametric Wilcoxon Rank-Sum test if normality is not satisfied.

Changes in exploratory endpoints (before and after treatment) will be quantified using means (95% CI) and/or medians (inter-quartile ranges) for non-normal data. Comparisons between the two arms will be made using two-sample independent t-tests or the non-parametric equivalent, Wilcoxon Rank-Sum test. The associations between baseline levels and/or changes over time of IL-8 and other key cytokines (TNF, IL-1b, IL-6) with outcomes will be assessed using regression models.

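### Between-arm changes in exploratory markers and NEWS2 are tested without adjusting for the baseline value already collected, which usually costs some precision

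*Combined protocol and SAP*

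**What the plan says.** Section 13.2 first describes the summary: "Changes in exploratory endpoints (before and after treatment) will be quantified using means (95% CI) and/or medians (inter-quartile ranges) for non-normal data". It then gives the test: "Comparisons between the two arms will be made using two-sample independent t-tests", with the Wilcoxon rank-sum test as the non-parametric alternative. No baseline covariate is named, and no ANCOVA or other baseline-adjusted model of change appears elsewhere in the document. Regression is planned for these biomarkers only to relate cytokines to outcomes: "IL-8 and other key cytokines (TNF, IL-1b, IL-6) with outcomes will be assessed using regression models".

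The endpoints concerned are listed as exploratory under Section 11.2. They include the inflammatory markers ("Changes in LDH, D-Dimer, CRP, ESR, NLR and absolute lymphocytes before and after treatment and over time will be measured every other day during hospitalization"), sIL-6, circulating cytokines and NEWS2 ("Changes in NEWS2 score will be reported at days 3, 5, 8, 11, 15, and 29").

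The baseline values exist. Section 10.1 and the Section 10 calendar require LDH, D-dimer, CRP, sIL-6, NLR, absolute lymphocyte count and NEWS2 at screening. ESR is the exception: Section 11.2 names it, but neither screening list includes it. Planned arm sizes are in Section 13.1: "N=92 patients randomized to the treatment arm and N=46 patients assigned to the standard of arm/control".

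**The concern.** Subtracting the baseline from the follow-up value is equivalent to assuming that the two are related with a slope of exactly 1. When the slope is lower, as is common for laboratory markers and scores, subtraction over-corrects and adds baseline noise to the comparison. ANCOVA estimates the slope from the data instead.

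Eligibility in Section 5.1 runs from low saturation on room air to mechanical ventilation. Section 7.5 describes a pre-generated 2:1 scheme and names no stratification factor. The arms may therefore differ by chance on a marker at baseline, and an unadjusted comparison leaves that difference in the estimate actually observed. What is at stake is the precision of the exploratory biomarker and NEWS2 comparisons, with 46 controls at most.

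**Working it through.** **No planned figure to reproduce.** The document states no SD, correlation, power or sample size for these comparisons.

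**Inputs.** From Section 13.1: 92 and 46 patients per arm. Assumed, because not given: baseline–follow-up correlation r from 0.3 to 0.9, and equal SDs at the two times unless stated otherwise.

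**General formulas.** With baseline SD s0 and follow-up SD s1, the variance of the arm difference is proportional to:

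- change score: s0² + s1² − 2·r·s0·s1
- ANCOVA: s1²·(1 − r²)

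The first minus the second is (s0 − r·s1)². In large samples ANCOVA is therefore never less precise. The two are equal only when r·s1/s0, the slope of follow-up on baseline, is 1.

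**Equal SDs (SD = 1).** The variances become 2(1 − r) and 1 − r². The 95% half-width is 1.9777 × √variance × √(1/92 + 1/46), and √(1/92 + 1/46) = 0.181.

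| r | Change score | ANCOVA | Reduction | Half-width, change (SD) | Half-width, ANCOVA (SD) |
|---|---|---|---|---|---|
| 0.3 | 1.40 | 0.91 | 35% | 0.423 | 0.341 |
| 0.5 | 1.00 | 0.75 | 25% | 0.357 | 0.309 |
| 0.7 | 0.60 | 0.51 | 15% | 0.277 | 0.255 |
| 0.9 | 0.20 | 0.19 | 5% | 0.160 | 0.156 |

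In interval width the ANCOVA/change ratio is √((1 + r)/2): 0.806, 0.866, 0.922 and 0.975. The change-score interval is thus about 24%, 15%, 8% and 3% wider.

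**Finite samples.** In 2,000 simulated trials per setting at 92 v 46 with equal SDs, the mean width ratio was 0.811 (r = 0.3), 0.871 (0.5), 0.926 (0.7) and 0.979 (0.9). ANCOVA gave the wider interval in 0%, 0%, 0.2% and 13% of datasets.

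**Where the gain vanishes.** With r = 0.667 and a follow-up SD 1.5 times the baseline SD, the slope is 0.667 × 1.5 = 1. The mean ratio was then 1.004, and ANCOVA was slightly wider in about 80% of datasets.

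**Chance imbalance.** The standard error of a baseline difference at 92 v 46 is 0.18 SD, so a difference at least that large is expected in about one trial in three. With r = 0.5 and equal SDs the slope is 0.5, and such a difference moves the observed change-score contrast by (1 − 0.5) × 0.18 = 0.09 SD. ANCOVA removes that shift.

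**The case against.** The strongest reply is that nothing here is wrong. A randomised comparison of change scores is valid, the endpoints are exploratory, and no decision rests on them. That stands, and it limits the point to precision.

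Three stronger readings are tempting, and the document does not support them.

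- *Chance baseline imbalance biases each estimate.* It does not. Over repeated randomisation the change-score difference is unbiased, and its standard error already allows for imbalance. The 0.09 SD shift above is conditional on the imbalance observed.
- *Skewed markers will be forced through a t-test.* Section 13.2 provides medians and the Wilcoxon test for non-normal data. If the markers are skewed, that route is likely to be used, and the variance ratios above do not carry over to it directly. What remains is that the Wilcoxon comparison of changes also makes no use of baseline as a covariate.
- *Separate tests at each visit discard patients as they are discharged.* Section 13.2 speaks of change before and after treatment and sets no visit-by-visit testing. The NEWS2 endpoint says only that changes are reported at six days.

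It is also fair that the 95% CIs in Section 13.2 belong to the mean changes. No interval for the difference between arms is specified, so the widths above describe the analysis the t-test implies, not an output the plan promises.

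**Conclusion.** The point holds as one of lost precision. The between-arm comparison of exploratory changes ignores a baseline value that is already available for NEWS2 and almost all the markers. On the t-test route with equal SDs, adjustment would lower the variance by between 35% (correlation 0.3) and 5% (correlation 0.9). The correlations and the equal-SD condition are assumptions, and the gain falls to nothing as the slope approaches 1. A reader might turn the 25% at correlation 0.5 into a general need for one third more patients (1/0.75 = 1.33). That figure belongs to that single assumed case.

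The primary log-rank test, its alpha, the event count and the sample size are untouched. This is a free improvement, not an error in the plan.

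**What to change.** In Section 13.2, replace the unadjusted test for the between-arm comparison of exploratory changes with ANCOVA, using the baseline value of the same measure as covariate. Analyse skewed markers on the log scale, with baseline logged too. Report the adjusted difference, or the adjusted ratio for logged markers, with its 95% CI. Keep the Wilcoxon rank-sum test on changes as a sensitivity analysis. The endpoint can still be called change from baseline: once baseline is in the model, the treatment effect is the same whether the response is the change or the follow-up value. The wording should name the follow-up day each model uses, since Section 13.2 does not.

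The cost is a few lines of analysis text. No visit, sample or patient is added. ESR can be adjusted only if a baseline value is in fact recorded.

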13.3 Subgroup Analysis

A post-hoc, subgroup analysis will be employed to compare the primary and secondary endpoints for cancer vs non-cancer patients.

A post-hoc, subgroup analysis based on severity of respiratory symptoms is also planned to investigate the consistency or heterogeneity of the treatment effect across the following pre-specified groups:

- 1) Severe Respiratory Disease – defined as oxygen saturation $\leq 93\%$ on room air, RR ≥ 24 or $\geq 50\%$ lung involvement on imaging within 24 - 48hrs.
- 2) Critical Respiratory Disease – defined as respiratory failure requiring non-rebreather, high-flow nasal cannula, ICU admission, non-invasive ventilation, invasive ventilation.

13.4 Interim analyses

One interim analysis is planned after approximately 17 (40% of the total 41 events) have been observed using O'Brien and Fleming stopping boundary using the Lan-DeMets spending function at a nominal type I error of 0.025. The intent-to-treat (ITT) principle is applied to the analysis, and therefore, we inflated the sample size by 5% to safeguard against drop-outs.

An independent Data Safety Monitoring Committee (DSMC) will serve as the primary reviewer of the results of the interim analyses of the study and will make recommendations for discontinuation of the study or protocol modifications. Stopping rules for overwhelming efficacy and/or futility are provided in Table 4 below.

Table 4. Efficacy and Boundaries and Properties for the Time to Improvement Analysis

Analysis*	Value	Efficacy	Futility
IA1: 40%	Nominal critical point Z-value	3.3569	0.0811
N: 138	p (1-sided)	0.0004	0.4677
Events: 17	~HR at bound	0.1720	0.9584
Month: 2.6	P(Cross) if HR=1	0.0004	0.5323
	P(Cross) if HR=0.4	0.0599	0.0427
IA2: 100%	Nominal critical point Z-value	1.9622	1.9622
N: 138	p (1-sided)	0.0249	0.0249
Events: 41	~HR at bound	0.5217	0.5217
Month: 7	P(Cross) if HR=1	0.0240	0.9760
	P(Cross) if HR=0.4	0.8000	0.2000

*This column displays the number of events and percentage (%) of needed time to improvement events, the expected sample size (N), and the estimated months (Month) after first participant is randomized for each analysis.

p (1-sided): the nominal α for testing.

~HR at bound: the approximate hazard ratio required to reach the bound for overwhelming efficacy or futility stop.

P (Cross if HR=1): the probability of crossing a bound at or before each analysis under the null hypothesis.

P (Cross if HR=0.40): the probability of crossing a bound at or before each analysis under the alternative hypothesis.

Abbreviations: HR = hazard ratio; IA = interim analysis.

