Statistical Methodology	This is a single center, randomized, open-label, phase 2 trial to evaluate the time-to-improvement in the 7 point ordinal scale following treatment with BMS-986253 compared to standard of care in hospitalized patients with COVID-19 respiratory disease. With a sample of 138 patients (N=92 patients randomized to the treatment arm and N=46 patients assigned to the control/standard of care arm), the study will have 80% power to detect an increase in the median time to improvement from 5 days (control) to 2 days (anti-IL-8 arm) with one-sided alpha of 0.025. The sample size was estimated based on a hazard ratio (HR) of 0.40 assuming an exponential survival.
Interim Analysis	One interim analysis is planned once 17 (40% of the total 41 events) have been observed using O'Brien and Fleming stopping boundary using the Lan-DeMets spending function and inflation for drop-outs. The intent-to-treat (ITT) principle is applied to the analysis, and therefore, we inflated the sample size by 5% to safeguard against drop-outs/lost-to-follow-up.

Protocol Schema:

Contents

Protocol Signature Page	4
1. Introduction	12
2. Study Objectives	12
Primary Objective	12
Secondary Objectives.....	12
2.1 Exploratory Objectives	13
3. Background	13
3.1 Disease Background.....	13
3.2. IL-8 is a key cytokine in the pathogenesis of coronavirus-associated ARDS.....	14
3.3. Rationale for anti-IL-8 therapy in hospitalized patients with severe COVID-19.....	15
Investigational AgentS	15
3.4 BMS-986253	15
4. Study Design	20
4.1 General Design.....	20
4.2 Number of Subjects.....	21
5. Subject Selection and Withdrawal	21
5.1 Inclusion Criteria	21
5.2 Exclusion Criteria	23
5.3 Inclusion of Women and Minorities	23
5.4 Subject Recruitment.....	23
5.5 Early Withdrawal of Subjects	24
6. REGISTRATION PROCEDURES	25
6.1 CUMC Research Participant Registration	25
6.2 Informed Consent Procedures.....	26
7. TREATMENT PLAN	27
7.1 Agent Administration.....	27
7.2 Management of Infusion Reactions:	28
7.3 General Concomitant Medication and Supportive Care Guidelines	29
7.4 Treatment Compliance.....	29
7.5 Randomization and Blinding	29
7.6 Duration of Therapy.....	30
7.7 Duration of Follow Up.....	30
7.8 Criteria for Removal from Study	30
DOSING DELAYS/ DOSE MODIFICATIONS.....	30
7.9 Criteria and Procedures for Dose Modifications and Interruptions	30

8.	ADVERSE EVENTS: LIST AND REPORTING REQUIREMENTS	32
8.1	Adverse events	32
8.2	Definitions.....	33

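### Table 4's 80% power at 41 events fits slower improvement on treatment; for the hypothesised faster improvement under 2:1 allocation it is about 67–72%

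*Combined protocol and SAP*

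**What the plan says.** The synopsis (Statistical Methodology) claims "80% power to detect an increase in the median time to improvement from 5 days (control) to 2 days (anti-IL-8 arm". Section 13.1 makes the same claim with the arms exchanged: "median time to improvement from 2 days (control) to 5 days (treatment arm". Both use the same effect size; in the words of 13.1, "The sample size was estimated based on a hazard ratio (HR) of 0.40 assuming an exponential survival distribution". Allocation is 2:1 (92 and 46 patients), the primary test is log-rank (13.2), and "The overall type I error for the primary analysis will be considered one-sided alpha of 0.025".

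Section 13.4 fixes the event counts: "One interim analysis is planned after approximately 17 (40% of the total 41 events) have been observed". Table 4 gives an interim efficacy bound of Z = 3.3569 and a futility bound of Z = 0.0811, a final bound of 1.9622, N = 138 at both looks (months 2.6 and 7), and a probability of 0.8000 of crossing for efficacy if HR = 0.4. Its hazard ratios at the efficacy bounds (0.1720 and 0.5217) are below 1. The documents do not say which arm is in the numerator, nor which formula gave 41 events.

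**The concern.** The event here is improvement, so a beneficial drug raises the hazard. With exponential times the hazard is ln 2 / median. The synopsis medians give a treatment-to-control ratio of (ln 2/2)/(ln 2/5) = 2.5; those in 13.1 give 0.40. Under equal allocation this would be a matter of labelling. Under 2:1 allocation it changes power, because it decides whether the larger arm has the events early or late. If 41 events was derived for the 13.1 direction, the 80% claim does not carry over to the benefit the trial is meant to detect, and a final analysis at 41 events would miss that benefit more often than the stated 20% of the time.

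**Working it through.** **Inputs.** One-sided alpha 0.025 and the log-rank test (13.2); HR 0.40, exponential times, 92:46 (13.1); medians from the synopsis and from 13.1; 17 and 41 events and the bounds (Table 4). The 5% drop-out allowance affects N, not power at a fixed event count. Accrual pattern and blocking are assumed.

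**1. Table 4's own figures.**
- A two-look normal calculation with the printed bounds at 40% information gives null crossing probabilities of 0.0004, 0.5323 and 0.0240, exactly as printed.
- The printed 0.0599, 0.0427 and 0.8000 under HR = 0.4 all correspond to a drift of 2.847.
- The hazard ratio at the final bound implies (1.9622/|ln 0.5217|)² × 9/2 = (1.9622/0.6507)² × 4.5 ≈ 40.9 events at 2:1.

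**2. Where 41 events and 80% come from.** The Lachin–Foulkes method (separate null and alternative variances), with the 3.3% inflation for the interim look, over a range of assumed control medians and accrual lengths, gives:
- treatment hazard 0.4 × control (slower improvement): 40.3–41.6 events, which matches the plan;
- treatment hazard 2.5 × control (faster improvement): 43.2–47.9 events, which does not.

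**3. Why direction matters at 2:1.** Take all patients at risk from the start and ignore depletion of the risk sets. The null share of events in the anti-IL-8 arm is 2/3, with variance 2/9 per event.
- Faster: share = 2 × 2.5/(2 × 2.5 + 1) = 5/6, about 34 of 41 events. Mean of Z = √41 × (5/6 − 2/3)/√(2/9) = 2.26; SD of Z = √[(5/36)/(2/9)] = 0.79. Power at the final bound ≈ Φ((2.26 − 1.96)/0.79) ≈ 0.65.
- Slower: share = 2 × 0.4/(2 × 0.4 + 1) = 4/9. Mean of |Z| = √41 × (2/3 − 4/9)/√(2/9) = 3.02; SD = √[(20/81)/(2/9)] = 1.05. Power ≈ Φ((3.02 − 1.96)/1.05) ≈ 0.84.

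This is a rough guide, but it shows the mechanism: the larger arm can exceed its two-thirds share of events by little (1/6) and can fall short of it by more (2/9).

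**4. Log-rank simulation with Table 4's bounds at events 17 and 41** (6,000–20,000 trials per scenario).

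| Scenario | Power |
|---|---|
| Faster (5 to 2 days), simultaneous entry | 67% |
| Faster, Table 4's timeline (41 of 138 with events at month 7) | 67% |
| Faster, simple randomisation | 68–69% |
| Faster, blocked, staggered entry | 71–72% |
| Slower (2 to 5 days), all entry patterns | 76–83% |

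**5. Events needed in the faster direction.** Simulated power is 78% at 50 events and about 83% at 55, with the interim kept at 40%. About 51–55 events therefore give 80% or slightly more.

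**6. Fit of events, N and medians.** With medians of 5 and 2 days and accrual spread over 1 to 12 months, the 41st event comes after about 43–64 enrolments (both directions considered), not 138. Conversely, if all 138 entered evenly by month 2.6 and 41 had improved by month 7, the faster-direction medians would have to be about 21.8 months (control) and 8.7 months (anti-IL-8), not days.

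**The case against.** **Table 4's arithmetic.** A reader might infer that Table 4 is simply miscalculated, because Schoenfeld's formula gives a drift of |ln 0.4| × √(41 × 2/9) = 2.766 and two-look power of 77.7%, with 43.5 events needed for 80%. The documents do not support that. They name no event formula, fixed-design Schoenfeld power at 41 events is 79.0%, and Lachin–Foulkes reproduces 41 events and 80% in one direction. The 77.7% reflects a choice of formula.

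**Section 13.1 is internally consistent.** For the medians written there, simulated power brackets 80%. This stands. The root fault is the conflict of direction between the synopsis and 13.1; the power shortfall is its consequence.

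**138 patients will supply more than 41 events.** This also stands, and limits the point. A reader might infer that 138 patients cannot give 80% power. That does not follow. In simulation of the synopsis effect, power is about 98% at 100 events with the interim moved to event 40. With the interim left at event 17 and its futility bound obeyed, a final look at 110 events gives about 92–93%; claims close to certainty would have to ignore that bound. But Table 4 makes 41 events the 100% analysis, and no section sets a later one.

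**Assumptions.** Accrual and blocking are assumed, which is why a range is given. The simulations also leave out deaths, although section 3.1 cites mortality of about 20–25% in severe disease.

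**Conclusion.** The concern holds in this form: 41 events with Table 4's bounds supports the 80% claim only for slower improvement on treatment. For the synopsis hypothesis, power at 41 events is about 67–72%, which is 8–13 points below the stated figure, so the planned benefit would be missed about 28–33% of the time. This rests on exponential medians of 5 and 2 days (for the Table 4 timeline row, the same hazard ratio), 92:46 allocation, assumed accrual and blocking, no deaths, and a final analysis at the 41st event. Separately, 41 events, N = 138 at both looks and medians measured in days do not fit together.

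A reader might also infer from efficacy bounds below HR 1 that the trial would declare success for slower improvement. The documents do not support this: the synopsis hypothesis is faster improvement, and the orientation of the ratio is undefined rather than shown to be reversed in the analysis.

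**What to change.** 1. Reconcile the medians in the synopsis and 13.1, correct the description of the effect as an increase, and say which arm is in the numerator of the hazard ratio.
2. Recompute the event count, bounds and power in Table 4 for an improvement HR of 2.5 with 2:1 allocation. Name the method, the accrual assumption and the randomisation scheme, and check power by log-rank simulation.
3. State the event count or follow-up point that triggers the final analysis of the 138 patients already planned, and make N and the calendar times in Table 4 agree with it. Waiting until all patients have completed day 28 is one option, not a necessary correction.
4. Restate the power with the interim futility bound included.

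The cost is a recalculation and replacement of the power statements and Table 4, before the interim analysis. No extra patients are needed.

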4.2 Number of Subjects

This study will enroll a total of 138 subjects randomized 2:1 (anti-IL-8: standard of care).

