7.7 Duration of Follow Up

Following completion of therapy, patient will have follow up by phone every 30 days for the first 100 days following the last dose of therapy. Patients will then have follow up by phone every 90 days (+/- 30 days) for up to 1 year. In addition, patients will be assessed 28 days (+/- 2 days) following start of treatment whether they are discharged or in the hospital. Participants who discontinue study treatment must continue to be followed for collection of outcome and/or survival follow-up data as required and in line with **Section 4.1** until death or the conclusion of the study.

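### Table 4's N of 138 at both looks cannot follow from 17 and 41 events with median times of 2 and 5 days, and the synopsis and section 13.1 give those medians to opposite arms

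*Combined protocol and SAP*

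**What the plan says.** The synopsis (Statistical Methodology) says the trial has 80% power to "detect an increase in the median time to improvement from 5 days (control) to 2 days (anti-IL-8 arm". Section 13.1 says it has 80% power to "detect an increase in median time to improvement from 2 days (control) to 5 days (treatment arm) with one-sided alpha of 0.025". Both use a hazard ratio of 0.40, one-sided alpha 0.025, 92 patients on treatment and 46 on control. Section 13.1 sizes the trial "assuming an exponential survival distribution with inflation to account for one interim look and 5% drop-out rate".

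Section 13.4 states: "One interim analysis is planned after approximately 17 (40% of the total 41 events) have been observed". Table 4 then gives, for the first look, N 138, 17 events, month 2.6, efficacy Z 3.3569 and HR at bound 0.1720. For the second look, labelled 100%, it gives N 138, 41 events, month 7, Z 1.9622 and HR at bound 0.5217. The footnote explains N and Month as "the expected sample size (N), and the estimated months (Month) after first participant is randomized for each analysis".

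Section 4.2 fixes enrolment: "This study will enroll a total of 138 subjects randomized 2:1". On follow-up, section 7.7 says "patients will be assessed 28 days (+/- 2 days) following start of treatment". On estimation, section 13.2 says "Cox regression will be employed to estimate the treatment effect (HR) and 95% CI" without naming the numerator. No accrual rate or accrual period is given anywhere; the synopsis gives only an estimated study duration of 12 months.

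**The concern.** Two things do not fit together.

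First, patients whose median time to improvement is 2 or 5 days produce events almost as fast as they enrol. A table with all 138 enrolled at month 2.6 but only 17 improved, and only 41 improved at month 7, belongs to a disease with a time scale of months.

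Second, the endpoint is time to improvement, so a longer time is a worse outcome. Both sections call the change an increase, but they assign the medians to opposite arms. The direction of benefit, and so the meaning of the HR bounds, is not fixed in the text.

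At stake are the planning information given to the monitoring committee, the event count or enrolment that triggers the final analysis, and the stated power. Allocation is 2:1, so power at a given event count depends on which arm improves faster.

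**Working it through.** **Inputs.** HR 0.40, one-sided alpha 0.025, 2:1 allocation, exponential medians of 2 and 5 days, 5% drop-out (section 13.1 and synopsis); 17 and 41 events, months 2.6 and 7, N 138 (Table 4). Accrual is not stated and is varied below. One month is taken as 30.44 days.

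**1. What reproduces.**
- Power at 41 events by Schoenfeld: Φ(√(41 × 2/9) × ln 2.5 − 1.96) = 79.0%, close to the stated 80%.
- O'Brien-Fleming-type spending at 40% information: cumulative alpha 0.00039, Z = 3.3569, as in Table 4.
- HR at the final bound: exp(−1.9622 / √(41 × 2/9)) = 0.522, as in Table 4.

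The event target and the Z-values are not at fault.

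**2. From 17 to 41 events with 138 enrolled (no accrual assumption).** With 138 − 17 = 121 at risk, and every one of them given the slower 5-day median, the expected time for 24 more events is the sum over i = 0 to 23 of 1 / ((121 − i) × ln 2 / 5) = 1.59 days. If 7 patients (5%) are already lost, 114 are at risk and the sum is 1.70 days. Table 4 allows 7 − 2.6 = 4.4 months, or 133.9 days.

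**3. Events expected by month 7.** If 138 are enrolled by month 2.6, each has at least 133.9 days of follow-up by month 7, which is 26.8 of the slower medians. Expected events are 92 × (1 − 2^(−133.9/m1)) + 46 × (1 − 2^(−133.9/m2)) = 138.0 for either assignment of the medians; × 0.95 = 131.1 if the 5% lost contribute none. Table 4 has 41. With follow-up cut at day 28 the figures are 136 to 137, or 129 to 130 after 5% loss.

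**4. If some patients never improve.** Section 3.1 cites mortality of about 20–25% in severe disease. Suppose 25% never improve and the medians apply to the rest (an assumption). Step 2 becomes about 2.3 days and step 3 about 103 events. The rows still do not fit.

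**5. Can the months be kept?** Yes, but not with N = 138. Reaching 17 events at month 2.6 and 41 at month 7 takes about 6 to 7 patients a month, so about 18 and 42 are enrolled at the two looks. At that steady rate 138 patients take about 20 to 23 months.

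**6. Direction.** As treatment over control, the 13.1 medians give a hazard ratio of 2/5 = 0.40 and the synopsis medians give 5/2 = 2.5. In the synopsis direction the efficacy bounds would be 1/0.1720 = 5.81 and 1/0.5217 = 1.92.

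**7. Enrolment when the 41st event occurs.** This is by simulation, with even accrual of 138 patients and 5% drop-out over 28 days (assumed), across both directions:

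| Accrual period | All improve | 25% never improve |
|---|---|---|
| 10 days | 83–93 | not used here |
| 20–365 days | 43–73 | about 57–89 |

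**8. Power at 41 events with Table 4's bounds** (same simulation, accrual 20–365 days). If all improve, it is about 70–72% in the synopsis direction and about 76–80% in the 13.1 direction. If 25% never improve, the synopsis direction falls to roughly 15–44%.

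**The case against.** The best defence is that N and Month are planning columns. The interim is triggered by events, the Z-boundaries are correct, and a committee reviewing the interim would see actual enrolment. N = 138 might simply be the planned total printed in both rows. This limits the harm but does not rescue the table: the footnote defines N as expected at each analysis, and step 5 shows what the months imply under the stated medians.

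Four stronger readings are tempting, and the documents do not support them.

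- **Half or more of the patients will be unenrolled at the final analysis.** This depends on accrual, which is not stated, and on everyone improving. With 10-day accrual, 83 to 93 are enrolled and 32–40% are not. It also assumes that 41 events triggers the final analysis. The words total and 100% in section 13.4 suggest this, but only the interim has an explicit trigger, and sections 4.2 and 13.1 fix enrolment at 138.
- **The trial is underpowered at about 70%, and a modestly higher event target would repair it.** Step 8 shows how strongly power at 41 events depends on the share who never improve. If all 138 are analysed, with about 130 events under the stated medians, Schoenfeld gives Φ(√(130 × 2/9) × ln 2.5 − 1.96), which is above 99%.
- **The interim boundary breaks type I error control.** If the final analysis had 130 events, 17 would be 13% information and the cited spending function would give Z of about 6.1 rather than 3.36. But keeping 3.3569 and 1.9622 gives a one-sided error of at most 0.0004 + 0.0249 = 0.0253. The effect is small.
- **The trial is designed to show slower recovery.** The objective is improvement, and no numerator is named for the hazard ratio, so 0.40 could be control over treatment. The text is contradictory; it does not establish that intent.

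**Conclusion.** The concern holds in two parts that need no accrual assumption. Table 4's combination of N, events and months is incompatible with the stated medians: 1.6 to 1.7 days against 4.4 months between looks, and about 131 to 138 events against 41 by month 7. The medians are also reversed between the synopsis and section 13.1, which leaves the direction of the HR bounds undefined.

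The rest is conditional. If 41 events triggers the final analysis and every patient eventually improves, about 43 to 73 of 138 would be enrolled at that point for even accrual over 20 to 365 days. Faster accrual, or patients who never improve, raises that number. A reader might infer a mix-up of time units, since N = 138 would fit a control median of about 7.6 months, but the documents do not confirm it.

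This must be fixed: it concerns a wrong design table and an undefined direction of effect for the primary test.

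**What to change.** 1. State one direction of effect in the synopsis and section 13.1, replace the word increase where it contradicts that direction, name the numerator of the hazard ratio, and restate Table 4's HR bounds to match.
2. State the accrual rate, the follow-up horizon for the primary endpoint and the expected proportion who improve. Re-run Table 4 so that N, events and months agree at both looks.
3. State whether the final analysis is at 41 events or after all 138 patients.
   - If at 41 events: correct N and months, say whether enrolment continues and how later events are used, and restate the power for the chosen direction together with its non-improver assumption.
   - If all 138 are analysed: recompute the total events, the information fraction at the interim and the bounds.

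The cost is one re-run of the design calculation and edits to the synopsis, 13.1 and 13.4, submitted to the IRB as a protocol modification. No new event target should be chosen until the non-improver assumption is stated; whether the target or the sample size then has to change depends on that assumption.
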